### 2.3.4. Potential Risks

The tolerability and safety profile of selexipag administered to SAPH patients is expected to be consistent with that in adult patients with PAH.

The short- and long-term safety profile of selexipag has been established in PAH patients in the AC-065A302 (GRIPHON) study conducted in 1,156 participants and is mainly characterized by prostacyclin-associated adverse events (AEs) associated with the mode of action of selexipag. Such AEs typically occur during the initial phase of individualized dose titration, and the susceptibility varies between individuals. Adverse reactions, reflecting the mode of action of selexipag, included headache, diarrhea, nausea and vomiting, jaw pain, myalgia, pain in extremity, arthralgia, and flushing.

Other AEs reported more frequently on selexipag compared to placebo included hypotension, anemia, hyperthyroidism, nasopharyngitis, nasal congestion, decreased appetite, weight decreased, rash, urticaria, and erythema.

Hypotension was reported more frequently in the selexipag group than in the placebo group (5.0% and 3.1%, respectively). In the selexipag group, 9.7% of patients had systolic blood pressure (SBP) <90 mm Hg on at least 1 occasion, compared to 6.7% in the placebo group. A decrease from baseline of >40 mm Hg in SBP was reported for 2.3% and 3.0% of patients in the selexipag and placebo groups, respectively.

Sinus tachycardia was reported more frequently on 12-lead electrocardiogram (ECG) with selexipag compared to placebo.

Hyperthyroidism was reported more frequently in the selexipag group compared to the placebo group. Corresponding laboratory changes were a small reduction in thyroid stimulating hormone (TSH) at most post-baseline visits.

Anemia was reported more frequently in the selexipag group, and a small reduction in hemoglobin was observed at most post-baseline visits.

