5.6.3. Additional Safety Assessments

5.6.3.1. Clinical Laboratory Tests

Clinical laboratory tests will be displayed for the participants included in the safety analysis set and will be presented by study treatment for the entire study period. Local laboratory data will be included in listings and used only to find marked abnormalities.

The laboratory tests are summarized in table below:

Laboratory Assessments	Variables
Hematology	Hemoglobin Hematocrit Erythrocyte count Platelet count Leukocyte count with differential: Neutrophils Lymphocytes Monocytes Eosinophils Basophils
Clinical Chemistry	Alanine aminotransferase Aspartate aminotransferase Alkaline phosphatase Total and direct bilirubin Creatinine Sodium, potassium Serum albumin Glomerular filtration rate, using the Modification of Diet in Renal Disease formula Thyroid hormones: Free and total triiodothyronine (T3) Free and total thyroxine (T4) Thyroid stimulating hormone (TSH)
Other Tests	A serum pregnancy test for women of childbearing potential will be performed at Screening. Urine pregnancy tests will be performed at randomization and monthly thereafter. Urine pregnancy tests are either performed on-site during a scheduled visit or at home with the pregnancy test validated kit provided by the site. The results of the urine pregnancy tests will not be collected in the eCRF. Results of pregnancy tests will be documented in the participant's records (pregnancy test card). The date of the urine pregnancy test reported on the pregnancy card will be collected in the eCRF. Additional serum or urine pregnancy tests may be performed, if pregnancy is suspected during the study, as determined necessary by the investigator or required by local regulation, to establish the absence of pregnancy at any time during the participation in the study. NT-proBNP will be analyzed as part of the efficacy assessments.

Descriptive statistics (including change from baseline) will be presented for all chemistry and hematology laboratory tests at scheduled time points by treatment group.

An abnormality (abnormality based on criteria defined in tables in [Appendix 10](#)) will be attributed to the baseline and postbaseline values.

Postbaseline abnormalities will be compared with their corresponding baseline result:

- Treatment emergent (TE) will be concluded if the postbaseline value is worse than the baseline value.

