- If the postbaseline value is above the upper limit and the baseline value is below the upper limit (eg, Normal or Low), then the postbaseline abnormality will be considered TE. The same applies to the postbaseline value being below the lower limit with the baseline value being above the lower limit (eg, Normal or High).
- If the baseline value is missing, a postbaseline abnormality will always be considered as TE.

Treatment-emergent marked laboratory abnormalities will be summarized for each laboratory variable for which marked abnormalities are defined providing their incidence and frequency.

In addition, the proportion of participants with the following treatment-emergent liver abnormalities will be summarized:

- ALT $\geq 3 \times$ upper limit of normal (ULN), ALT $\geq 5 \times$ ULN, ALT $\geq 8 \times$ ULN
- AST $\geq 3 \times$ ULN, AST $\geq 5 \times$ ULN, AST $\geq 8 \times$ ULN
- ALT or AST $\geq 3 \times$ ULN, ALT or AST $\geq 5 \times$ ULN, ALT or AST $\geq 8 \times$ ULN
- ALT or AST $\geq 3 \times$ ULN and concomitant (collected on the same day) bilirubin $\geq 2 \times$ ULN and both (ALT or AST and bilirubin) increased compared to baseline
- ALT or AST $\geq 3 \times$ ULN and bilirubin $\geq 2 \times$ ULN at any time and both (ALT or AST and bilirubin) increased compared to baseline

All laboratory data will be listed together with derived marked abnormality flag. A separate listing of marked abnormality laboratory values will be provided.

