6.8. Appendix 8 Adverse Events of Special Interest

The following adverse events of special interest will be used for selexipag. These are based on the important identified and potential risks in the latest Risk Management Plan and on-going discussion with Pharmacovigilance Risk Assessment Committee.

AE Special Interest Category
Anaemia
Bleeding events
Gastrointestinal disturbances denoting intestinal intussusception (manifested as ileus or obstruction)
Hyperthyroidism
Hypotension
Light-dependent non-melanoma skin malignancies
Major adverse cardiovascular events (MACE)
Medication errors
Ophthalmological effects associated to retinal vascular system
Pregnancy
Pulmonary venoocclusive disease associated with pulmonary oedema
Renal function impairment / acute renal failure
Prostacyclin associated reactions*

*Prostacyclin associated reactions will be summarized separate from other AESIs

A specific file containing all preferred terms for each category as per last coding version will be maintained.

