6.10. Appendix 10 Laboratory Toxicity Grading

The grading scale use for lab assessments is based on tables below.

Blood chemistry marked abnormalities (SI Units)				
Laboratory test name (CDISC Synonym[s])	LL	LLL	HH	HHH
Alanine aminotransferase	NA	NA	$> 3 \times \text{ULN}$	$> 5 \times \text{ULN}$
Aspartate aminotransferase	NA	NA	$> 3 \times \text{ULN}$	$> 5 \times \text{ULN}$
Alkaline phosphatase	NA	NA	$> 2.5 \times \text{ULN}$	$> 5 \times \text{ULN}$
Bilirubin; Total bilirubin	NA	NA	$> 2 \times \text{ULN}$	$> 5 \times \text{ULN}$
Creatinine	NA	NA	$> 1.5 \times \text{ULN}$	$> 3 \times \text{ULN}$
Sodium	NA	$< 130 \text{ mmol/L}$	$> 150 \text{ mmol/L}$	$> 155 \text{ mmol/L}$
Potassium	$< 3.2 \text{ mmol/L}$	$< 3.0 \text{ mmol/L}$	$> 5.5 \text{ mmol/L}$	$> 6.0 \text{ mmol/L}$

CDISC = Clinical Data Interchange Standards Consortium; NA = not applicable; ULN = upper limit of normal.

Blood chemistry marked abnormalities (SI Units)				
Laboratory test name (CDISC Synonym[s])	LL	LLL	HH	HHH
Hemoglobin	$< 100 \text{ g/L}$	$< 80 \text{ g/L}$	$> 20 \text{ g/L above baseline}$	$> 40 \text{ g/L above baseline}$
Hematocrit; EVF; PCV (male)	$< 0.32 \text{ L/L}$	$< 0.20 \text{ L/L}$	$> 0.60 \text{ L/L}$	$> 0.65 \text{ L/L}$
Hematocrit; EVF; PCV (female)	$< 0.28 \text{ L/L}$	$< 0.20 \text{ L/L}$	$> 0.55 \text{ L/L}$	$> 0.65 \text{ L/L}$
Platelets (assuming no platelet cluster)	$< 75 \times 10^9/\text{L}$	$< 50 \times 10^9/\text{L}$	$> 600 \times 10^9/\text{L}$	$> 999 \times 10^9/\text{L}$
Leukocytes; white blood cells	$< 3.0 \times 10^9/\text{L}$	$< 2.0 \times 10^9/\text{L}$	$> 20.0 \times 10^9/\text{L}$	$> 100.0 \times 10^9/\text{L}$
Neutrophils (Abs)	$< 1.5 \times 10^9/\text{L}$	$< 1.0 \times 10^9/\text{L}$	NA	NA
Eosinophils (Abs)	NA	NA	$> 5.0 \times 10^9/\text{L}$	NA
Lymphocytes (Abs)	$< 0.8 \times 10^9/\text{L}$	$< 0.5 \times 10^9/\text{L}$	$> 4.0 \times 10^9/\text{L}$	$> 20 \times 10^9/\text{L}$

CDISC = Clinical Data Interchange Standards Consortium; EVF = erythrocyte volume fraction; NA = not applicable; PCV = packed cell volume.

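### SAP Appendix 10 has no criterion for TSH, T3 or T4, so thyroid tests get no laboratory-based count of treatment-emergent abnormalities by arm

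*SAP*

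**What the plan says.** SAP 5.6.3.1 lists five thyroid tests under clinical chemistry: free and total T3, free and total T4, and TSH. All chemistry tests get descriptive statistics with change from baseline by treatment group. For abnormalities the section points to one source: "An abnormality (abnormality based on criteria defined in tables in" Appendix 10. The summary rule is: "Treatment-emergent marked laboratory abnormalities will be summarized for each laboratory variable for which marked abnormalities are defined providing their incidence and frequency".

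Appendix 10 opens with "The grading scale use for lab assessments is based on tables below". The first table covers chemistry and the second covers hematology. Neither has a thyroid row.

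On the risk itself, Protocol 2.3.4 says of the earlier PAH trial: "Hyperthyroidism was reported more frequently in the selexipag group compared to the placebo group". It adds: "Corresponding laboratory changes were a small reduction in thyroid stimulating hormone (TSH) at most post-baseline visits". SAP Appendix 8 names "Hyperthyroidism" as an adverse event of special interest, and Protocol 2.3.5 gives thyroid function tests as an example of the safety monitoring. Marked laboratory abnormalities that emerge on treatment are a stated safety endpoint (Protocol 3, SAP 1.1).

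**The concern.** The plan collects five thyroid tests because of a named risk, then defines no threshold for any of them. An analyst who follows the SAP will produce the marked-abnormality table without a thyroid row and will be right to do so. The report would then have no objective answer, by arm, to the question of how many participants developed a low TSH or a raised thyroid hormone.

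The remaining by-arm count, of reported adverse events, depends on investigators. Under Protocol Appendix 2 the investigator marks whether an abnormal value is clinically relevant, and only relevant ones become adverse events. A count from the central laboratory values does not pass through that judgment.

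**Working it through.** No sample size, power or alpha figure is involved. The check matches the tests in SAP 5.6.3.1 to the rows of Appendix 10 and then applies the SAP's own rule.

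1. **Chemistry, 15 variables listed.** Seven have a row: ALT, AST, alkaline phosphatase, total bilirubin, creatinine, sodium and potassium. The other 15 − 7 = 8 do not: direct bilirubin, serum albumin, glomerular filtration rate and the five thyroid tests.
2. **Hematology, 10 variables listed.** Seven have a row: hemoglobin, hematocrit, platelets, leukocytes, neutrophils, eosinophils and lymphocytes. The other 10 − 7 = 3 do not: erythrocytes, monocytes and basophils.
3. **Total.** 7 + 7 = 14 of 25 variables can be counted, and 11 cannot. Thyroid: 0 of 5.
4. **Other routes in SAP 5.6.3.1.** The extra proportions in that section concern ALT, AST and bilirubin only. The text on upper and lower limits decides whether an abnormality is treatment-emergent. It works on abnormalities that Appendix 10 has already defined, so it supplies no thyroid criterion. Local laboratory data serve only for listings and for finding marked abnormalities, so a local thyroid result reaches no by-arm summary either.
5. **Against the protocol.** Protocol 9.5.2 commits to reference ranges and SAP-specified markedly abnormal results, and to frequency tables of abnormalities. For thyroid tests the SAP gives neither. SAP Appendix 2, on changes to planned analyses, does not mention this.
6. **Against comparable risks.** The safety endpoints give three examples of adverse events of special interest:

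| Example | Objective criterion in the SAP |
|---|---|
| Hypotension | Table 6: systolic below 90 mm Hg with a fall of more than 30; diastolic below 50 mm Hg with a fall of more than 20 |
| Anemia | Appendix 10: hemoglobin below 100 g/L and below 80 g/L |
| Hyperthyroidism | None |

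Protocol 2.3.4 pairs anemia with a small hemoglobin fall and hyperthyroidism with a small TSH fall. Only the first pair has a laboratory threshold.

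**The case against.** **The thyroid data are far from unreported.** This stands. SAP 5.6 requires N, mean, SD, median, minimum and maximum by arm for every continuous safety variable, and SAP 5.6.3.1 applies descriptive statistics with change from baseline to the thyroid tests. All values are listed. SAP 5.6.2 counts each adverse event by arm, including hyperthyroidism, and lists events of special interest.

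A reader might infer that a few strongly affected participants would be invisible in these tables. They would not be. Assume, for illustration only, an arm of 12 in which k participants fall from TSH 2.0 to 0.05 mIU/L (a change of −1.95) and the rest do not change. The mean change is −1.95k/12, and the SD is the square root of (k × 1.95² − 12 × mean²)/11.

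| k | Mean change | SD | Minimum change | Affected |
|---|---|---|---|---|
| 1 | −0.16 | 0.56 | −1.95 | 8% |
| 2 | −0.33 | 0.76 | −1.95 | 17% |
| 3 | −0.49 | 0.88 | −1.95 | 25% |

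The minimum and SD would alert the reader. What the table does not state is the number affected: the minimum is the same in all three rows.

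**The documents do not say that the effect is confined to a strongly affected minority.** This also stands. They describe a small TSH reduction at most visits, which a mean change can show. The point does not rely on any such pattern.

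**Partial coverage is expected, and the study stopped early.** The rule does foresee tests without criteria, and 11 of 25 have none. Most of the others are not tied to a named risk in the protocol as TSH is. Early termination reduced efficacy to listings but kept by-arm laboratory statistics, marked-abnormality counts and liver proportions, so it does not explain the missing thyroid rows. It does mean that the counts will be small and that the listings can be read participant by participant.

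**Conclusion.** The point holds as a minor gap. Under the SAP's rule, none of the five thyroid tests gets a by-arm count of treatment-emergent abnormalities, although the protocol promises frequency tables and names hyperthyroidism with a TSH fall as a risk.

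A reader might go further and conclude that hyperthyroidism has no by-arm count at all, or that thyroid safety is not analyzed. The documents do not support that: reported events are counted, and the laboratory values are both summarized and listed. Only the laboratory-based count is missing.

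The conclusion rests on reading Appendix 10 as complete. Nothing in it suggests a redaction or a cut. The preferred-term file behind the special-interest categories is not in the documents, so it cannot be said which laboratory-type terms it would capture.

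**What to change.** Add to SAP 5.6.3.1 and Appendix 10 a count and percentage of participants, by arm, with treatment-emergent values outside the central laboratory reference range:

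- TSH below the lower limit.
- Free T3, total T3, free T4 and total T4 above the upper limit, one row each.
- A combined flag: TSH below the lower limit with free T3 or free T4 above the upper limit on the same day. Count it when the combination is present after baseline and was absent at baseline.

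The existing treatment-emergence rule can be used for the five single-test rows. Say whether local results enter the count. The documents give no thyroid cut-offs beyond the promise to use reference ranges, so any further grades of marked abnormality are for the sponsor to set.

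Fix the criteria before the final database lock (SAP 1.2.1). Asking for this before unblinding may not be possible. SAP 1.2.3 keeps the blind only until the study is stopped prematurely, and the decision to stop (26 Sep 2022) came before SAP version 3.0 (01 December 2022).

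Cost: 5 + 1 = 6 table rows on data already collected. The downside is more rows to review, with small counts.

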5.6.3.2. Vital Signs and Physical Examination Findings

Vital signs will be displayed for the participants included in the safety analysis set and will be presented by study treatment for the entire study period.

Continuous vital sign parameters including weight, pulse, blood pressure (systolic and diastolic), and Body Mass Index (BMI) will be summarized at each assessment time point. Body Mass Index will be calculated as weight (kg)/(height (m))², at each time point that body weight is measured. The height measurement collected at [screening/the nearest visit] will be used in the calculation. Change from baseline will be summarized. Descriptive statistics (mean, standard deviation, median, minimum and maximum) will be presented.

Abnormality criteria (based on criteria defined below in [Table 6](#)) will be applied to baseline and postbaseline values. For baseline values, increase or decrease criteria are not applied.

Postbaseline values will be considered treatment-emergent if they meet both value and change criteria in the [Table 6](#) below. If the baseline value is missing, a postbaseline abnormality will always be considered as treatment-emergent.

Incidence of treatment-emergent clinically important vital signs during intervention, as defined in [Table 6](#), will be summarized for participants who had a baseline assessment and at least 1

postbaseline assessment for that vital sign. A listing of participants with treatment-emergent clinically important vital signs will be presented, along with a listing of all vital sign measurements.

Table 6 Clinically Important Vital Signs

Vital Sign	Criteria
Pulse	>120 bpm and with >30 bpm increase from baseline
	<50 bpm and with >20 bpm decrease from baseline
Systolic blood pressure	>180 mm Hg and with >40 mm Hg increase from baseline
	<90 mm Hg and with >30 mm Hg decrease from baseline
Diastolic blood pressure	>105 mm Hg and with >30 mm Hg increase from baseline
	<50 mm Hg and with >20 mm Hg decrease from baseline

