18. Treatment with moderate inducers of CYP2C8, eg, rifampicin or strong inhibitors of CYP2C8, eg, gemfibrozil at or within 14 days prior to randomization.

19. Change in dose or initiation of new diuretics and/or calcium channel blockers within 1 week prior to RHC qualifying for enrollment.

20. SBP <90 mmHg at Screening or at randomization.

21. Known allergies, hypersensitivity, or intolerance to selexipag or its excipients (refer to [IB selexipag](#)).

22. Planned or current treatment with another investigational intervention up to 90 days prior to randomization.

23. Criterion deleted per Amendment 3

24. Any condition for which, in the opinion of the investigator, participation would not be in the best interests of the participant (eg, compromise well-being), or that could prevent, limit, or confound the protocol-specified assessments.

25. Criterion modified per Amendment 3

25.1 Any acute or chronic impairment that may influence the ability to comply with study requirements such as to perform RHC, a reliable and reproducible 6MWT, or lung function tests.

a Note: The assessment of hepatic impairment (Child-Pugh Score) must be fully documented for patients who have clinical signs and evidence (from central and/or local lab) of hepatic impairment (see Section 10.13).

26. Employee of the investigator or study site, with direct involvement in the proposed study or other studies under the direction of that investigator or study site, as well as family members of the employees or the investigator.
27. Pregnant, breast-feeding, or planning to become pregnant while enrolled in this study or within 30 days after the last dose of study intervention.

**NOTE:** Investigators should ensure that all study enrollment criteria have been met at Screening. If a participant's clinical status changes (including any available laboratory results or receipt of additional medical records) after Screening but before randomization such that he or she no longer meets all eligibility criteria, then the participant should be excluded from participation in the study. The required source documentation to support meeting the enrollment criteria are noted in Section 10.3, Regulatory, Ethical, and Study Oversight Considerations.

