5.1.3. Baseline

Baseline is defined as the last observation on or before the day of first dose of study treatment.

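### SAP Table 6 leaves out systolic readings below 90 mm Hg in participants with baseline 90–119 unless they have fallen by more than 30 mm Hg; a value-only count should be added

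*SAP*

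**What the plan says.** The low-systolic row of Table 6 in SAP section 5.6.3.2 reads "<90 mm Hg and with >30 mm Hg decrease from baseline". The text above the table makes the conjunction explicit: "Postbaseline values will be considered treatment-emergent if they meet both value and change criteria". At baseline only the value part is used: "For baseline values, increase or decrease criteria are not applied". The resulting output is the "Incidence of treatment-emergent clinically important vital signs during intervention", restricted to participants with a baseline and at least one later reading, together with a listing of those flagged.

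SAP section 5.1.3 fixes the reference point: "Baseline is defined as the last observation on or before the day of first dose of study treatment". Protocol section 5.2, criterion 20, excludes "SBP <90 mmHg at Screening or at randomization".

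Protocol section 2.3.4 reports the large PAH trial of selexipag with the value and the change kept apart. In the selexipag group, "9.7% of patients had systolic blood pressure (SBP) <90 mm Hg on at least 1 occasion", against 6.7% on placebo. A systolic fall of more than 40 mm Hg was seen in 2.3% on selexipag and 3.0% on placebo.

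Section 5.6.3.2 provides other vital-sign output as well: descriptive statistics at each time point including minimum and maximum, the statement "Change from baseline will be summarized", and a listing of every measurement.

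**The concern.** A rule that needs both a low value and a large fall is normally used to separate new low readings from stable ones. In this trial the entry criterion already does much of that work. Participants start at 90 mm Hg or above, barring protocol deviations, so a reading below 90 on study is almost always a new crossing. The change part then removes crossings reached by a moderate fall, and it removes them only from participants who started below 120.

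The same SAP treats the matching situation differently for laboratory tests. In section 5.6.3.1, a post-baseline value below the lower limit is treatment-emergent when the baseline was above that limit, with no minimum size of change.

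What is at stake is whether the by-arm vital-sign table shows how many participants reached a systolic pressure below 90. In the PAH trial that measure was more frequent on selexipag. Because Table 6 makes a fall of more than 30 mm Hg compulsory, its count cannot be set beside either systolic figure in Protocol section 2.3.4.

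**Working it through.** The documents give no expected count or rate for this flag, so there is no planned figure to reproduce. The check works through the rule itself.

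**Inputs.** Value limit 90 and fall limit 30 mm Hg (SAP Table 6); both required (SAP 5.6.3.2); lowest permitted entry SBP 90 (Protocol 5.2, criterion 20).

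**Step 1: what the rule requires.** With baseline B and post-baseline reading S, a flag needs S < 90 and B − S > 30. This is the same as S < min(90, B − 30), or a fall greater than max(30, B − 90). On the value alone, the fall needed is greater than B − 90.

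| Baseline B | Table 6 flags S below | Fall needed, Table 6 | Fall needed, value only |
|---|---|---|---|
| 90 | 60 | >30 | >0 |
| 95 | 65 | >30 | >5 |
| 100 | 70 | >30 | >10 |
| 110 | 80 | >30 | >20 |
| 119 | 89 | >30 | >29 |
| 120 | 90 | >30 | >30 |
| 130 | 90 | >40 | >40 |
| 150 | 90 | >60 | >60 |

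**Step 2: which readings are dropped.** A reading below 90 goes unflagged when B − S ≤ 30, so B ≤ S + 30 < 120. Every dropped reading therefore comes from a baseline below 120. From 120 upwards the two rules coincide. Examples: 110 to 82 is a fall of 28 and 95 to 70 is a fall of 25, and neither is counted.

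**Step 3: illustrative size.** The documents give no systolic mean, SD or correlation, so these are assumptions. Take baseline and one later reading as bivariate normal with mean 120, SD 15, correlation 0.6 and a mean shift of −5. Given B, the later reading has mean 120 + 0.6(B − 120) − 5 and SD 15√(1 − 0.36) = 12.

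- B = 100: mean 103. Table 6: Φ((70 − 103)/12) = Φ(−2.75) = 0.30%. Value only: Φ((90 − 103)/12) = Φ(−1.08) = 13.9%.
- B = 110: mean 109. Table 6: Φ((80 − 109)/12) = 0.78%. Value only: Φ((90 − 109)/12) = 5.7%.
- B = 120: mean 115. Both rules: Φ((90 − 115)/12) = 1.86%.
- B = 130: mean 121. Both rules: Φ((90 − 121)/12) = 0.49%.

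Seven settings were tried, with mean 115–125, SD 15–18, correlation 0.5–0.9 and shift −5 or −15. At B = 100 the value-only probability ran from 12.4% to 40.1%, against 0.002% to 2.8% under Table 6. The size depends heavily on the assumptions; the thresholds in step 1 do not.

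**Step 4: scale in this trial.** At the full planned 37 per arm, the PAH rates would give 37 × 0.097 = 3.6 against 37 × 0.067 = 2.5 participants with SBP below 90, and 37 × 0.023 = 0.9 against 37 × 0.030 = 1.1 with a fall above 40. The terminated study is smaller.

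**The case against.** The two-part rule is a deliberate and consistent choice. All six rows of Table 6 have the same structure, and the table claims to show clinically important treatment-emergent values, not to define hypotension. Protocol section 9.5.2 promises only descriptive statistics of values and changes for vital signs, so no commitment is broken. Without the change part, a move from 91 to 89 counts as an event. All of this stands, which is why the present row should stay.

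It is also true that low pressure is reported elsewhere. Treatment-emergent adverse events are tabulated by arm, hypotension is a category of special interest in SAP Appendix 8, and section 5.6.3.2 gives minima at each visit and lists all readings. That limits the harm but does not replace the count. A minimum at a visit does not say how many participants went below 90. Adverse-event reporting is a different measure: in the PAH trial hypotension events were 5.0% against 3.1%, while readings below 90 were 9.7% against 6.7%.

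With so few participants, a listing may serve nearly as well as a percentage. This stands as a limit on the benefit, not as a reason to avoid one extra row.

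**Conclusion.** The point holds as a sensitivity limit of one descriptive safety table. Table 6 does not count readings below 90 mm Hg reached by a fall of 30 mm Hg or less, and these come only from baselines of 90–119. The thresholds follow from the documents alone; the probabilities rest on an assumed blood-pressure distribution. The practical impact is modest.

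Three stronger readings are not supported.

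- A reader might infer that participants who start low are the least likely to be flagged. The fall required is smallest, above 30, for every baseline from 90 to 120 and grows beyond that. If change is independent of baseline (mean −5, SD 15), 4.8% are flagged at each baseline from 90 to 120 and 0.14% at 140. With regression to the mean (the setting in step 3), it is 0.10% at 90 and 0.02% at 150. In no setting tried was 90 the single lowest.
- A reader might infer that the SAP undercounts hypotension in general. The omission concerns the Table 6 incidence and its listing only.
- A reader might take the share of participants with baseline at or below 115 as the share of events missed at a reading of 85. With a normal baseline, SD 15, cut off at 90, that share is 59%, 35% or 16% for means of 110, 120 or 130. It describes an assumed baseline distribution and treats a reading of 85 as equally likely from every starting value, so it measures neither missed events nor bias between arms.

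**What to change.** Keep the present low-systolic row and add one row to Table 6: *SBP <90 mm Hg at any post-baseline visit, regardless of change*, with n/N (%) by arm. Use the same participants and observation period as the existing row, and exempt the new row from the requirement that both criteria be met.

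A further row for a fall of more than 40 mm Hg is optional. Its only use is comparison with Protocol section 2.3.4, where that measure showed no excess on selexipag (2.3% against 3.0%).

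The cost is one table row from data already collected. The downside is lower specificity, because small drifts across 90 are counted; showing both rows lets the reader separate these from the larger falls. This is a change in reporting only and touches no rule for managing participants.
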